# 7.6. Data management

#### 7.6.1. Data collection method

Data for this study shall be collected using a specific case report form provided by Sponsor. Investigator will complete promptly after observation period and submit them to the Sponsor.

#### 7.6.2. Patient registration

#### 7.6.2.1. Procedure of patient registration

#### (1) Registration

The following information regarding registration should be recorded in the registration forms if this product is given to patients who meet the following registration criteria; patients should be registered via FAX at the registration center until the target number of patients is registered. Patients should be registered via FAX within 2 weeks from the initiation of administration of this product with the start date of administration as Day 1.

- 1) Registration criteria
- Patients who have not developed invasive fungal infection at the initiation of administration with this product
- Patients who received hematopoietic stem cell transplantation or patients who plan to receive hematopoietic stem cell transplantation
- 2) Registration data

Patient identification number, sex, age at the initiation of administration, date on which administration of this product begins and eligibility to registration criteria

[ Patient Registration Center ]

[contact] (Accessible 24 hours a day)

# (2) Exclusion from the registration

Patients found to not meet the registration criteria after the registration form is received at the registration center will be excluded from the registration.

#### 7.6.3. Reminders concerning completion, revision, and submission of case report form

# **7.6.3.1.** Completion

The investigator shall, upon confirming the study items, complete the CRF based on medical charts and other medical records such as relevant test results, using an ineffaceable ink such as ballpoint pen.

#### 7.6.3.2. Revision

Upon receiving Sponsor's inquiry on the contents of the CRF (query forms), the investigator will again confirm the contents of medical records described earlier, and as required, correct relevant sections and resubmit the form. Corrections in the CRF should be struck out with a double line (=) with a "correction seal" on the double line; the double line should be drawn so that the original contents prior to correction are legible.

#### **7.6.3.3.** Submission

CRFs should be submitted promptly upon completion in accordance with the procedures set out by Sponsor.

# 7.7. Data analysis

The details of analysis method on data collected in this study shall be described in the Statistical Analysis Plan to be separately prepared.

# 1) Definition of analysis set

The safety analysis set shall include patients for whom the registration in this study and administration of this product have been confirmed and the safety has been evaluated.

The effectiveness analysis set shall include patients for whom the presence/absence of invasive fungal infections has been evaluated among the safety analysis set.

- 2) Analysis method
- (1) Safety analysis

The number of patients who developed each adverse reaction and the proportions will be tabulated. Also, for patients who developed major investigation items of hepatic toxicity and visual events, differences between patients who can continuously receive this product and patients who must discontinue the administration of this product will be analyzed experimentally.

#### (2) Effectiveness analysis

The proportion of patients who developed invasive fungal infections (the number of patients with proven diagnosis + the number of patients with probable diagnosis/number of patients for effectiveness analysis excluding undeterminable patients  $\times$  100), proportion of patients with successful prophylaxis of invasive fungal infections (the number of patients without onset of invasive fungal infections/the number of patients for effectiveness analysis excluding undeterminable patients  $\times$  100), and each 95% CI will be calculated for effectiveness analysis set. Also, the analysis using the survival analysis method (Kaplan-Meier method) will be performed.

Detailed methodology for summary and statistical analyses of data collected in this study will be documented in a Statistical Analysis Plan (SAP), which will be dated, filed and maintained by the Sponsor. The SAP may modify the plans outlined in the protocol; any major modifications of primary endpoint definitions or their analyses would be reflected in a protocol amendment.

# 7.8. Quality control

Pfizer staff in charge of site will explain the contents of the protocol, etc. to the investigator prior to the implementation of this study and ask the investigator to prepare a case report form based on medical charts.

#### 7.9. Limitations of the research methods

The following matters are considered for this study:

- 1) Since no control group is set in the study, there is a limit to the judgment on whether or not a risk of developing adverse events and adverse reactions increases due to the administration of the study drug.
- 2) The consideration for confounding factors may not be adequate because the background information may not be sufficiently obtained.
- 3) Since this is a study that collects the information described in medical charts, the set data may not be collected or there may be missing information.

#### 7.10. Other aspects

N/A

#### 8. PROTECTION OF HUMAN SUBJECTS

#### **8.1.** Patient Information and Consent

All parties will ensure protection of patient personal data and will not include patient names on any sponsor forms, reports, publications, or in any other disclosures, except where required by laws. In case of data transfer, Pfizer will maintain high standards of confidentiality and protection of patient personal data.

In this study, the information will be collected by transcribing medical chart information described in routine medical practice. In doing so, the informed consent will not be used because the information collected from medical charts is anonymized and does not contain any information that identifies individual patients.

#### 8.2. Patient withdrawal

Patients may withdraw from the study at any time at their own request, or they may be withdrawn at any time at the discretion of the investigator or sponsor for safety, behavioral, or administrative reasons. In any circumstance, every effort should be made to document outcome, if possible. The investigator should inquire about the reason for withdrawal and follow-up with the patient regarding any unresolved adverse events.

# 8.3. Institutional Review Board (IRB)/Independent Ethics Committee (IEC)

In this study, the review by the IRB/IEC is not essential.

# **8.4.** Ethical Conduct of the Study

This study is excluded from the patient since it includes the scope of application of the "Good Post-Marketing Study Practice" (Ordinance of Ministry of Health, Labour and Welfare No. 171 of December 20, 2004)

#### 9. MANAGEMENT AND REPORTING OF ADVERSE EVENTS/ADVERSE REACTIONS

The handling of each event in the case where the investigator becomes aware of any event concerning the safety information should be prescribed as follows:

For an event that needs to be reported to the Sponsor within 24 hours, the investigator must report it using the designated "Non Interventional study AE Report Form (hereinafter referred to as "NIS AE Report Form").

At the initiation of study, each staff in charge of each site shall request each investigator to report events that need to be reported within 24 hours of discovery, and visit the investigator periodically within the study period to request for reporting.

The NIS AE Report Form will be handled as part of the case report form.

# 9.1. REQUIREMENTS

The table below summarizes the requirements for recording safety events on the case report form and for reporting safety events on the non-interventional study (NIS) adverse event monitoring (AEM) Report Form to Pfizer Safety. These requirements should be described for the following 3 types of events.(1) serious adverse events (SAEs); (2) non-serious AEs (as applicable); and (3) scenarios involving exposure to a Pfizer product, including exposure during pregnancy, exposure during breast feeding, medication error, overdose, misuse, extravasation, and occupational exposure. These events are defined in the section "Definitions of safety events".

Safety event	Recorded on the case report form	Reported on the NIS AEM Report Form to Pfizer Safety within 24 hours of awareness
SAE	All	All
Non-serious AE	All	None

Safety event	Recorded on the case report form	Reported on the NIS AEM Report Form to Pfizer Safety within 24 hours of awareness
Scenarios involving exposure to a Pfizer product, including exposure during pregnancy, exposure during breast feeding, medication error, overdose, misuse, extravasation; lack of efficacy; and occupational exposure	All (regardless of whether associated with an AE), except occupational exposure	All (regardless of whether associated with an AE) involving exposure to a Pfizer product

For each AE, the investigator must pursue and obtain information adequate both to determine the outcome of the adverse event and to assess whether it meets the criteria for classification as a SAE (see section "Serious Adverse Events" below)

Safety events must be reported to Pfizer within 24 hours of awareness of the event by the investigator as described in the table above. In particular, if the SAE is fatal or life-threatening, notification to Pfizer must be made immediately, irrespective of the extent of available event information. This timeframe also applies to additional new (follow-up) information on previously forwarded safety event reports. In the rare situation that the investigator does not become immediately aware of the occurrence of a safety event, the investigator must report the event within 24 hours after learning of it and document the time of his/her first awareness of the events.

For those safety events that are considered serious or that are identified in the far right column of the table above that are reportable to Pfizer within 24 hours of awareness, the investigator is obligated to pursue and to provide any additional information to Pfizer in accordance with this 24-hour timeframe. In addition, an investigator may be requested by Pfizer to obtain specific follow-up information in an expedited fashion. This information is more detailed than that recorded on the case report form. In general, this will include a description of the adverse event in sufficient detail to allow for a complete medical assessment of the case and independent determination of possible causality. Information relevant to the event, such as concomitant medications and illnesses must be provided. In the case of a patient death, a summary of available autopsy findings must be submitted as soon as possible to Pfizer or its designated representative.

# 9.2. Reporting period

For each patient, the safety event reporting period begins at the time of the patient's first dose of this product, and lasts through the end of the observation period of the study, which must include at least 28 calendar days following the last administration of a drug under study; a report must be submitted to Pfizer Safety (or its designated representative) for any of the types of safety events listed in the table above occurring during this period. If a patient was administered a drug under study on the last day of the observation period, then the reporting period should be extended for 28 calendar days following the end of observation.

If the investigator becomes aware of a SAE occurring at any time after completion of the study and s/he considers the SAE to be related to this product, the SAE also must be reported to Pfizer Safety.

# 9.3. Causality assessment

The investigator is required to assess and record the causal relationship. For all AEs, sufficient information should be obtained by the investigator to determine the causality of each adverse event. For AEs with a causal

relationship to this product, follow-up by the investigator is required until the event and/or its sequelae resolve or stabilize at a level acceptable to the investigator, and Pfizer concurs with that assessment.

An investigator's causality assessment is the determination of whether there exists a reasonable possibility that this product caused or contributed to an adverse event. If the investigator's final determination of causality is "unknown" and s/he cannot determine whether this product caused the event, the safety event must be reported within 24 hours.

If the investigator cannot determine the etiology of the event but s/he determines that this product did not cause the event, this should be clearly documented on the case report form and the NIS AEM Report Form.

#### 9.4. DEFINITIONS OF SAFETY EVENTS

#### 9.4.1. Adverse events

An AE is any untoward medical occurrence in a patient administered a medicinal product. The event need not necessarily have a causal relationship with the product treatment or usage. Examples of adverse events include but are not limited to:

- · Abnormal test findings (see below for circumstances in which an abnormal test finding constitutes an adverse event);
- · Clinically significant symptoms and signs;
- · Changes in physical examination findings;
- · Hypersensitivity;
- · Progression/worsening of underlying disease;
- · Lack of efficacy;
- · Drug abuse;
- · Drug dependency.

Additionally, for medicinal products, they may include the signs or symptoms resulting from:

- · Drug overdose;
- · Drug withdrawal;
- · Drug misuse;
- · Off-label use;
- · Drug interactions;
- · Extravasation;
- Exposure during pregnancy;
- · Exposure during breast feeding;
- · Medication error;
- · Occupational exposure.

#### Abnormal test findings

The criteria for determining whether an abnormal objective test finding should be reported as an adverse event are as follows:

- Test result is associated with accompanying symptoms, and/or
- · Test result requires additional diagnostic testing or medical/surgical intervention, and/or
- Test result leads to a change in study dosing or discontinuation from the study, significant additional concomitant drug treatment, or other therapy, and/or
- Test result is considered to be an adverse event by the investigator or sponsor.

Merely repeating an abnormal test, in the absence of any of the above conditions, does not constitute an adverse event. Any abnormal test result that is determined to be an error does not require reporting as an adverse event.

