#### 7.3.4.2. Laboratory tests

Input the following test items and test items for adverse events.

[Observation items] White blood cell count, neutrophil count, platelet count, total bilirubin, AST, ALT, Al-P, GGT, CRP, BUN, serum creatinine

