#### (1) Hepatic toxicity

For patients who developed events related to hepatic toxicity including abnormal hepatic function test values, assess the occurrence status and the differences in patient background, dose, etc. between patients who can be continuously administered this product and patients who must be discontinued administration of this product.

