#### 7.5.2. Rationale for sample size

It was considered that the following evaluations were possible if the target sample size was set to be 200 patients in total; 100 patients each for children and adults.

Safety perspectives:

In the phase 3 study of prophylactic administration of Vfend in foreign patients with HSCT (study A1501073), the incidence of adverse reactions classified into the SOC of hepatobiliary disorders was 20.2% (47/233 patients). Of those, one patient was led to discontinuation of administration of this product. In the phase 3 study of secondary prophylactic administration of Vfend in foreign patients with HSCT (study A1501038), the incidence of adverse reactions classified into the SOC of hepatobiliary disorders was 24.4% (11/45 patients). Of those, two patients were led to discontinuation of this product. Also, in the clinical study of Vfend conducted in Japanese children (from 2 years old to under 15 years old) (study A1501096), the incidence of adverse reactions related to hepatic toxicity including abnormal hepatic function test values was 19.0% (4/21 patients). Of those, two patients were led to discontinuation of this product. Based on the above, the incidence of hepatic toxicity in patients administered this product for prophylaxis of invasive fungal infections was similar between Japanese and foreign patients and it was considered that such incidence was also similar between adults and children.

In the case where the number of patients to be collected for the special investigation for prophylactic administration of Vfend for invasive fungal infections is set to be 200 patients and the incidence of hepatic toxicity is presumed to be 20%, it is estimated that at least 31 patients with hepatic toxicity will be accumulated at a probability of about 95%. With the cumulation of this sample size, it was considered possible to compare and review the proportion of patients who discontinued the administration of this product with the clinical studies.

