8.2.3.3. Other Endpoints

• Laboratory test values

In patients with hepatic toxicity, an adverse drug reaction considered as a major investigation item, summary statistics of the values of laboratory parameters related to hepatic function (AST, ALT, Al-P, and γ -GTP) at the initiation of treatment, the onset of the adverse drug reaction, and the completion of treatment will be calculated by change in treatment with Vfend. A1.1 Definition of Visit Timing of Appendix 10.1 will be followed for values at the initiation and completion of treatment. The value immediately before the day of onset of adverse drug reaction after the day of initiation of Vfend treatment will be used as the value at onset.

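### Entry to the hepatic-event set depends partly on whether treatment was changed or stopped, so the continue-versus-discontinue comparison is open to outcome-dependent ascertainment

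*Protocol*

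**What the plan says.** **The question.** For hepatic toxicity, including abnormal liver-function values, Protocol 7.3.8 (1) asks for "the differences in patient background, dose, etc. between patients who can be continuously administered this product and patients who must be discontinued". Protocol 7.7 and SAP 8.2.3.1 (Major investigation items) carry this forward as a comparison within patients who have the event. Protocol 7.5.2 also expects enough hepatic cases to "compare and review the proportion of patients who discontinued the administration of this product with the clinical studies".

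**The entry rule.** Protocol 9.4.1 (Abnormal test findings) lists criteria, any one of which makes a test result an adverse event:
- symptoms go along with it;
- it calls for more diagnostic work-up or for an intervention;
- "Test result leads to a change in study dosing or discontinuation from the study";
- it brings substantial further drug or other treatment;
- the investigator or sponsor considers it an adverse event.

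Repeating a test, with none of these met, does not qualify.

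**The hepatic check item.** Protocol 7.3.8.1.1 asks for presence or absence of hepatic toxicity, naming raised ALT, AST and GGT. New or worsened cases go to the adverse event column. No grade or cut-off is given.

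**The laboratory data.** Protocol 7.3.4.2 collects "White blood cell count, neutrophil count, platelet count, total bilirubin, AST, ALT, Al-P, GGT, CRP, BUN, serum creatinine". SAP 8.2.3.3 uses the liver tests in a restricted group: "In patients with hepatic toxicity, an adverse drug reaction considered as a major investigation item, summary statistics of the values". Its parameters are AST, ALT, Al-P and GGT, without total bilirubin. For other patients the values appear only in the laboratory listing (SAP 9).

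**The concern.** Whether treatment was changed or stopped is the outcome being compared, and it is also one of the ways into the set where the comparison is made. Take two patients with the same asymptomatic ALT rise. If the rise leads to a dosing change or discontinuation, it is an adverse event by that fact. If treatment goes on unchanged, with no work-up and no added therapy, it is one only if somebody judges it so.

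If some continuers of this kind go unrecorded, three results are affected:
- the proportion discontinuing among hepatic cases is too high;
- the recorded incidence of hepatic toxicity is too low;
- the recorded continuers may not represent all continuers, which would distort the background and dose contrast.

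The SAP offers no check, because its liver-test summary starts from patients already classed as having a hepatic reaction. The limitations in Protocol 7.9 do not mention this selection.

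**Working it through.** **1. The plan's own figure.** Protocol 7.5.2 expects at least 31 hepatic cases among 200 patients at 20% incidence, with probability about 95%. The exact binomial gives P(X ≥ 31 | n = 200, p = 0.20) = 0.957. The figure reproduces.

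**2. Routes into the hepatic set (Protocol 9.4.1).**

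| Situation | Adverse event under 9.4.1? |
|---|---|
| Rise with symptoms | Yes, whether treatment continues or stops |
| Rise needing further diagnosis or intervention | Yes, whether treatment continues or stops |
| Rise leading to significant added drug or other therapy | Yes, whether treatment continues or stops |
| Rise leading to a dosing change or discontinuation | Yes, by that fact |
| Asymptomatic rise, no work-up, no added therapy, no dosing change | Only if the investigator or sponsor considers it one |

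Only the last two rows separate patients by what happened to treatment. The asymmetry is therefore real, but it is confined to that last group of continuers. The criterion speaks of discontinuation from the study; stopping the drug is covered if it is read as a change in dosing.

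**3. Later filter.** Adverse drug reactions also need the physician's judgement of relatedness (SAP 6.1); missing causality counts as related (SAP 7). This applies to stoppers and continuers alike.

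**4. Direction and possible size.** Let d be the true share who stop among patients with comparable rises, and c the share of continuers who are recorded, with all stoppers recorded. Then

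observed share = d / (d + (1 − d) × c),

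which is at least d for any c ≤ 1.

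Inputs for d come from Protocol 7.5.2: 1 of 47, 2 of 11 and 2 of 4 hepatic cases discontinued (2.1%, 18.2%, 50%). Pooled, this is (1 + 2 + 2)/(47 + 11 + 4) = 5/62 = 8.1%, exact 95% CI 2.7% to 17.8%. The documents give no value for c, so the values below are assumptions.

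| Assumed c | Pooled, 5/(5 + 57c) | Observed share |
|---|---|---|
| 1.0 | 5/62 | 8.1% |
| 0.9 | 5/56.3 | 8.9% |
| 0.7 | 5/44.9 | 11.1% |
| 0.5 | 5/33.5 | 14.9% |

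At c = 0.5 the shift is 14.9 − 8.1 = 6.8 percentage points.

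**5. Against sampling error.** With 31 cases and 3 stoppers (9.7%), the exact 95% CI is 2.0% to 25.8%. The shifts in step 4 lie inside that width.

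**The case against.** **The check item may already capture continuers.** Protocol 7.3.8.1.1 applies to all study patients, names raised ALT, AST and GGT, and sets no condition about action taken. A missing threshold makes recording vary between sites but does not by itself tie it to stopping. This stands in part: some continuers will be recovered. But the parent heading (7.3.8.1) describes the item as confirming adverse events, which points back to 9.4.1, and the text does not say which rule governs.

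**Continuers have other routes in, and stoppers are not guaranteed entry.** Both are true. A reader might infer that continuers enter only by judgement, or that every stopper is in the reaction set. The documents support neither: symptoms, work-up and added therapy also admit continuers, and the reaction set requires relatedness.

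**All-cause data exist.** SAP 8.2.3.2 tabulates adverse events of any cause, and SAP 9 lists safety-specification events and laboratory values. This is correct, but the event tables rest on the same 9.4.1 entry rule, and a listing is not an analysis.

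**The reaction set matches the earlier studies.** Their figures in Protocol 7.5.2 are also based on adverse reactions, so a laboratory-defined set would not be like for like. This stands, and the reaction set should remain the one used for that comparison. It does not help the contrast within this study.

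**The yield of 31 cases.** A reader might infer that under-recording defeats it. The documents do not support this, because the presumed 20% follows from reported adverse reactions, not from a rate of laboratory elevations.

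**Conclusion.** The concern holds in a limited form. Entry to the hepatic set depends partly on the outcome later compared, through one group: continuers with an asymptomatic rise and no further action. Any under-recording of that group, with stoppers recorded, raises the observed proportion discontinuing.

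The size cannot be computed from the documents. The range of 8.9% to 14.9%, against 8.1%, rests on two assumptions: that the pooled earlier studies give the true share, and that 50% to 90% of continuers and all stoppers are recorded. That recorded continuers would be the more severe ones is plausible but not shown.

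The comparison is exploratory (Protocol 7.7, SAP 4.1), so no error rate is affected and no stated sample-size figure fails. An exploratory label does not remove the bias, however, and this is one of the study's two major investigation items. The missing total bilirubin is a separate, smaller gap: jaundice and hepatic failure are named hepatic events in Protocol 7.3.8.1.1.

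**What to change.** **In SAP 8.2.3.3:**
1. Add a supplementary table for the whole safety analysis set, using the collected AST, ALT, Al-P, GGT and total bilirubin, regardless of adverse event reporting.
2. Define a case by the first on-treatment value that crosses prespecified multiples of the pre-treatment value in Appendix A1.1, and of the site reference limit where available. The first crossing is preferable to the maximum on-treatment value, because continuers are observed longer and have more chances of a high maximum.
3. Tabulate discontinuation after that first crossing, with background and dose, beside the adverse-drug-reaction set. Keep the latter for comparison with the earlier studies.
4. Add total bilirubin to the existing parameter list.

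**In the plan's text:** state how Protocol 7.3.8.1.1 and 9.4.1 fit together for a liver-test rise without further action.

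**Cost:** one or two tables from data already collected.

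**Limits to state with the table:**
- Test frequency and length of observation differ between stoppers and continuers; anchoring on the first crossing reduces this but does not remove it.
- Protocol 7.3.7 asks for site reference values only for laboratory-related adverse events, so unrecorded continuers may have none.
- A multiple of baseline can lie within the normal range.
- Some elevations will have other causes.
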